**Table 4 Actions in Patients with Low Platelet Count or Drop in Platelet Count**  
*Continued*

Platelet Count on Rx	Drug Dose	Monitoring
100K/mm  - > 75K/mm 	Permanently reduce dose frequency to 300 mg every 2 weeks	
75K/mm  - > 50K/mm 	If occurs while on dose of 300 mg every 2 weeks then permanently discontinue Study Drug, otherwise dose pause When platelet count returns to > 100K/mm  restart dosing at dose frequency of 300 mg every 2 weeks only if approved by Sponsor Medical Monitor	Monitor every 2-3 days until 2 successive values are > 75K/mm  then monitor every 1 week Consider discontinuation of antiplatelet agents/NSAIDS/ anticoagulant medication
≤ 50K/mm 	
 
• Permanently discontinue Study Drug
 
	
 
• Monitor daily until 2 successive values show improvement then monitor every 2-3 days until 2 successive values are > 75K/mm^3 then monitor every 1 week
 
• Patient should be evaluated by a hematologist to provide diagnostic and therapeutic management
 
• Steroids recommended*. It is strongly recommended that, unless the patient has a medical contraindication to receiving glucocorticoids, the patient receives glucocorticoid therapy to reverse the platelet decline.
 
• Monitor triglyceride levels weekly and continue AE monitoring during steroid therapy
 
• Discontinue antiplatelet agents/NSAIDS/ anticoagulant medication while platelet count is < 50K/mm^3 if possible
 

\*\* Recovery in platelet count may be accelerated by administration of high dose corticosteroids. Treatment guidelines for immune thrombocytopenia ([Provan et al. 2010](#)) recommend dexamethasone 40 mg daily for 4 days every 2-4 wk for 1-4 cycles; prednisolone 0.5-2 mg/kg/day for 2-4 weeks then taper; or methylprednisolone 30 mg/kg/day for 7 days (**note:** may require continuation with oral corticosteroids after methylprednisolone)

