#### **10.6.4 Pharmacokinetic and Immunogenicity Analysis**

PK analysis will include the following:

- To determine trough (pre-dose) and post-treatment ISIS 304801 plasma concentrations in all patients who receive Study Drug. For all patients who receive ISIS 304801 treatment, trough (pre-dose) and post-treatment ISIS 304801 plasma concentrations will be summarized by treatment period, dose and Study Day, with and without stratification by immunogenicity status, using descriptive statistics

Immunogenicity (IM) analyses will include the following:

- To evaluate IM (confirmed positive/negative and, when applicable, titer of anti-ISIS 304801 antibodies) before, during, and after treatment with Study Drug in all evaluable patients and appropriately summarize by treatment period, treatment and dose over time
- To determine the IM incidence (number) and incidence rate (percent) at each evaluated study time point, and for the overall treatment and post-treatment evaluation period and summarize by treatment period, treatment and dose, as the total number of and percent of evaluated patients with antibody negative, positive, and unknown status
- Study patients with positive anti-ISIS 304801 antibody status may be further classified (when applicable) as being either 'persistent', 'transient', or not determinable
- To evaluate potential relationships of immunogenicity with selected efficacy, safety, and PK measures

Additional details regarding the PK and immunogenicity analysis will be described in the SAP.

Population PK and covariate analysis may be performed if deemed appropriate, and results will be reported separately.

Additional details regarding the PK analysis will be described in the SAP.

[REDACTED]

[REDACTED]

[REDACTED]

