### **3.2.2 Patient Population Analyzed**

The following analysis sets will be used for the analysis of data as described within each analysis set.

**Full Analysis Set (FAS):** All patients who are randomized and received at least 1 dose of Study Drug in the randomized treatment period, and who have a baseline fasting triglyceride assessment (see definition in Section 3.2.3 for fasting lipid measurements). The FAS represents the practically-feasible intent-to-treat population as delineated in ICH Guideline E9.

Patients for whom the blind is broken during the trial will not be excluded from the FAS population. Patients will be analyzed in the treatment group to which they were randomized. Efficacy endpoint collected in both Randomized Treatment Period and OLE Period will be analyzed in FAS by the treatment group to which they were randomized. Although all patients receive volanesorsen during OLE period, assessment during OLE period will be analyzed according to the treatment assigned at previous Randomized Treatment Period. For example, if patient is assigned to the Placebo treatment at the Randomized Treatment Period, this patient will be analyzed in Placebo treatment group for both Randomized Treatment Period and OLE period.

**Safety Set 1 (SAF1):** All patients who are randomized and receive at least 1 dose of Study Drug (volanesorsen or Placebo) in the Randomized Treatment Period.

Patients will be analyzed in the actual treatment group patients received during the Randomized Treatment Period. Patients randomized to receive placebo, but incorrectly treated with volanesorsen will be counted in the volanesorsen group for the whole study period.

**Safety Set 2 (SAF2):** All patients who enter the OLE Period and receive at least 1 dose of Study Drug (volanesorsen) in the OLE Period.

As patients all receive volanesorsen in OLE period. In SAF 2, patients will be analyzed by the actual treatment received in the Randomized Treatment Period.

**PK Population:** All patients who are randomized, receive at least 1 dose of volanesorsen, and have at least one evaluable PK data, in either Randomized Treatment Period or OLE Period.

Patients will be analyzed in the actual treatment group patients received. Patients randomized to receive placebo, but incorrectly treated with volanesorsen will be counted in the volanesorsen group for the whole study period.

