**Plasma PK Sampling Schedule**

Week	Wk 1	Wk 4	Wk 8	Wk 13	Wk 19	Wk 26	Wk 32	Wk 38	Wk 44	Wk 52
Study Day	1	22	50	85	127	176	218	260	302	358
Visit Window +/- Days	0	2	2	2	2	2	2	2	2	2
	Pre-dose									

Patients continuing to first year of OLE period

Week	Wk 56	Wk 60	Wk 65	Wk 71	Wk 78	Wk 84	Wk 90	Wk 96	Wk 104	Wk 110	Wk 117
Study Day	386	414	449	491	540	582	624	666	722	764	813
Visit Window +/- Days	2	2	2	2	2	2	2	2	2	7	7
	Pre-dose	Anytime	Anytime								

Patients continuing to second year of OLE period

Week	Wk 108	Wk 112	Wk 117	Wk 123	Wk 130	Wk 136	Wk 142	Wk 148	Wk 156	Wk 162	Wk 169
Study Day	750	778	813	855	904	946	988	1030	1086	1128	1177
Visit Window +/- Days	2	2	2	2	2	2	2	2	2	7	7
	Pre-dose	Anytime	Anytime								

Plasma concentrations of volanesorsen, along with the scheduled (nominal) and actual sampling times (i.e., time from SC dosing) will be listed (when applicable) for each patient, by treatment, patient ID, patient anti-drug antibody (ADA) status, and IM onset (if applicable) as defined in Section 3.6.2, and day. Plasma concentrations below the lower limit of quantification (LLOQ) will be presented as “0.00”.

For all patients who receive volanesorsen treatment, trough (pre-dose) and post-treatment volanesorsen plasma concentrations will be summarized by study day, with and without stratification by IM status (positive/negative or unknown), using descriptive statistics (n, mean, SD, SEM, %CV, geometric mean, geometric %CV, median, minimum, and maximum). For the purpose of calculating typical descriptive statistics for plasma concentrations, all below the lower limit of quantification (BLQ) values will be set to zero. Mean plasma concentrations that are BLQ will be presented as BLQ, and the SD and %CV will be reported as “NA” (not applicable). At the discretion of the pharmacokineticist and/or biostatistician, samples may be excluded from descriptive statistics if there are large deviations between scheduled and actual sampling times, or large deviations between actual dose and nominal dose.

Mean ( $\pm$ SD) plasma volanesorsen concentration-time plots with stratification by anti-drug antibody status will be generated on semi logarithmic scales.

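### SAP 3.6.1 summarises plasma concentrations by study day alone, so its Day 813 row averages post-treatment samples with on-treatment troughs; OLE arm and dosing frequency are left unspecified

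*SAP*

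**What the plan says.** Protocol 10.6.4 states that "plasma concentrations will be summarized by treatment period, dose and Study Day, with and without stratification by immunogenicity status". SAP 3.6.1 opens the matching sentence with "For all patients who receive volanesorsen treatment" and continues that "trough (pre-dose) and post-treatment volanesorsen plasma concentrations will be summarized by study day, with and without stratification by IM status". Treatment period and dose no longer appear. SAP 3.8 lists three departures from the protocol: no Per Protocol Set, reduced and altered efficacy analyses, and no disease burden score. The PK grouping is not among them.

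The SAP's Plasma PK Sampling Schedule has three parts: the randomised period, OLE year 1 and OLE year 2. The part headed "Patients continuing to first year of OLE period" ends with two samples that may be taken at any time, Day 764 (Week 110) and Day 813 (Week 117). The OLE year 2 part also contains Week 117 / Day 813, there as a pre-dose sample.

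Under SAP 3.2.2 the PK Population is made up of randomised patients with at least one dose of volanesorsen who "have at least one evaluable PK data, in either Randomized Treatment Period or OLE Period". Placebo patients therefore join it once they start drug in the OLE. The grouping rule is "Patients will be analyzed in the actual treatment group patients received". For Safety Set 2, the same section is more specific: "patients will be analyzed by the actual treatment received in the Randomized Treatment Period".

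For one band of platelet counts, Protocol Table 4 says "Permanently reduce dose frequency to 300 mg every 2 weeks". The SAP allows for that schedule when it defines safety analysis periods (3.7) and compliance (3.7.5), but not in 3.6.1.

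**The concern.** A trough or post-treatment concentration can be interpreted only if the reader knows how long the patient has been treated, at what interval, and how long ago the last dose was. Study day carries that information only while every patient sampled on that day is in the same state. If they are not, the row's mean, SD and geometric mean describe no real group of patients, and a dip in the mean concentration-time plot could reflect who was sampled and not the drug. The version stratified by antibody status would inherit the same mixture. Because SAP 3.8 is silent, a reader of the study report would also not know that the protocol's grouping had been replaced.

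**Working it through.** **1. Wording side by side.** Protocol 10.6.4: treatment period, dose, study day, with and without immunogenicity status. SAP 3.6.1: study day, with and without IM status. Two grouping variables are lost.

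**2. Schedule check.** In the SAP schedule, study day = 7 × (week − 1) + 1. This holds for all 32 entries (10 randomised, 11 OLE year 1, 11 OLE year 2), which give 31 distinct days. Week 104 is 7 × 103 + 1 = 722, and Week 117 is 7 × 116 + 1 = 813. The gap is 813 − 722 = 91 days, or 13 weeks.

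Comparing the pre-dose days with the any-time days, exactly one day is in both sets: Day 813. No randomised-period day coincides with an OLE day. Visit windows create no further overlap: the closest other pairs are Day 764 with Days 750 and 778, each 14 days apart, against combined windows of 7 + 2 = 9 days.

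**3. Exposure of OLE patients.** Prior scheduled weekly doses at an OLE year 1 pre-dose sample are (week − 53) for a former placebo patient and (week − 1) for a continuing volanesorsen patient.
- Day 386 (Week 56): 56 − 53 = 3, against up to 56 − 1 = 55.
- Day 722 (Week 104): 104 − 53 = 51, against up to 104 − 1 = 103.

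The gap is 52 doses throughout, and it matters most early, before new starters approach steady state.

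**4. What the protocol's words would repair.**
- *Treatment period* would split Day 813, provided post-treatment counts as its own period.
- It would not split former placebo from continuing patients, who are in the same OLE period on the same day. That needs the randomised arm.
- *Dose* is 300 mg per injection under both schedules, so it separates weekly from every-2-week dosing only if it is defined to include frequency.

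**5. Illustration of size at Day 813.** The documents give neither a half-life nor the mix of patients. Assume log-linear decline with half-life T of 2 to 5 weeks, a share p of post-treatment samples of 25% to 75%, and the same underlying weekly trough in both groups. A trough is 1 week after a dose and the post-treatment sample is 13 weeks after, so the post-treatment value is f = 2^(−12/T) of the trough. The pooled arithmetic mean, as a fraction of the trough, is 1 − p + p × f.

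| T (weeks) | f | p = 0.25 | p = 0.50 | p = 0.75 |
|---|---|---|---|---|
| 2 | 0.016 | 0.75 | 0.51 | 0.26 |
| 3 | 0.0625 | 0.77 | 0.53 | 0.30 |
| 4 | 0.125 | 0.78 | 0.56 | 0.34 |
| 5 | 0.189 | 0.80 | 0.59 | 0.39 |

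Under these assumptions the Day 813 row would show about 26% to 80% of the on-treatment trough.

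**The case against.** The strongest reply is that this concerns one nominal day in a descriptive table. Per-patient listings, which SAP 3.6.1 requires with actual time from dosing, keep all the information, and Protocol 10.6.4 leaves population PK open. That is fair as to scale. It does not make the Day 813 row right.

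Four stronger readings are tempting, and the documents do not support them.

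- *The whole profile mixes troughs with post-treatment samples.* It does not. Only Day 813 carries both kinds of scheduled sample. Days 22 to 358 hold randomised-period troughs, and Days 764, 1128 and 1177 are purely post-treatment, so the approach to steady state and the later decline can still be read there, subject to any mixing of arm or dosing frequency.
- *Day 449 is a second collision.* Week 65 ends follow-up for patients who do not enter the OLE, but that comes from the adverse event collection rules (Protocol 9.4.1 and 9.4.2). Neither the SAP schedule nor Protocol Appendix C lists a separate PK sample for those patients.
- *Dropping the protocol's words causes new starters to be pooled with one-year-treated patients.* The protocol's grouping would pool them too. The PK Population rule might even separate them; unlike the Safety Set 2 rule, it does not name the period that decides the group.
- *Every-2-week patients are bound to be pooled.* SAP 3.6.1 lets the pharmacokineticist or biostatistician exclude samples with large deviations in sampling time or dose, and a 14-day trough might be caught. But that clause is discretionary, concerns deviations and not a permitted schedule, and does not reach the Day 813 post-treatment samples, which are on schedule.

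**Conclusion.** The point holds in a limited form. The SAP replaces the protocol's grouping for plasma concentrations without declaring it, and its own schedule makes one row, Day 813 of 31 scheduled days, an average of two exposure states if both kinds of patient are sampled. Mixing of former placebo with continuing patients in the OLE, and of weekly with every-2-week dosing, is a risk left open by the text and not a stated outcome.

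The 26% to 80% range rests entirely on the assumed half-life and mix. SAP 3.1 and 3.8 say that study treatment was discontinued before the protocol-specified period was complete, so how many patients reach Day 813 in either state is unknown, and the real effect could be nil. The primary analysis, power and type I error are untouched. The change is worth making because it is cheap and removes a misleading row.

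**What to change.** In SAP 3.6.1, summarise and plot concentrations by:

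1. treatment period: randomised, OLE year 1, OLE year 2, and post-treatment, the last shown by time since last dose and not by study day;
2. treatment sequence in the OLE: volanesorsen then volanesorsen, or placebo then volanesorsen;
3. dosing frequency at the time of sampling: weekly or every 2 weeks;
4. study day within these, with and without antibody status.

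Items 2 and 3, and the use of time since last dose, go beyond the wording of Protocol 10.6.4, because that wording alone would not clearly resolve the mixing. State in SAP 3.2.2 which period's treatment defines a patient's group in the PK Population. Record in SAP 3.8 any grouping that still differs from Protocol 10.6.4.

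The cost is SAP wording and grouping variables that can be built from the dosing data already collected. The downside is small cells in a small trial, more so once antibody status is added; where a cell is too small to summarise, show individual values.

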### **3.6.2 Anti-drug Antibody**

Samples collected for anti-drug antibody (ADA) assessment at selected time points will be analyzed for anti-volanesorsen antibodies (i.e., anti-drug antibodies; ADA). Samples will be designated ‘ADA positive’ based on both positive screening and confirmation assay results (i.e., confirmed positive result), and otherwise be deemed ‘ADA negative’. Patients will be given ‘positive’ subject ADA status if they have at least one confirmed positive sample at any time before or during the treatment or post-treatment evaluation periods. Patients will be given ‘negative’ subject ADA status if all evaluated ADA sample results during the treatment and post-treatment evaluation periods are negative and they have at least one evaluable ADA result post-dose. Otherwise, patients will be given ‘unknown’ subject ADA status.

Sample ADA status (screen positive/negative, confirmed positive/negative or unevaluable, and when applicable, titer of anti-volanesorsen antibodies) before, during, and after treatment with Study Drug (volanesorsen or placebo) will be listed by treatment.

Patient ADA status (positive/negative or unknown) for all evaluable patients, along with the study day associated with the first positive ADA status emerged ( $T_{\text{first}}$ , i.e., onset of ADA development), the last positive ADA status observed ( $T_{\text{last}}$ ), the time of last evaluable ADA sample collected ( $T_{\text{last sampling}}$ ), and max titer, will be listed by treatment.

Additionally, the ADA incidence (number) and incidence rate (percent) at each evaluated time point will be summarized by treatment, as the total number and percent of evaluated patients with antibody negative, positive, and unknown status. Similarly, the ADA incidence and incidence rate at patient level will be summarized by treatment. Furthermore, onset, and max titer of the ADA response, if applicable, will be summarized as median, quartiles (25% and 75%), range by treatment for patients with positive ADA status.

Potential relationships between anti-drug antibody results (e.g., ADA status) and AE incidence will be evaluated in an exploratory manner.

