All primary, secondary [REDACTED] efficacy endpoints will be assessed in the FAS. Safety measures at Randomized Treatment Period and Randomized Treatment Period Post-Treatment Follow-up will be analyzed in SAF1. Safety assessment at OLE Period and OLE Post-Treatment Period will be analyzed in SAF2. PK endpoints will be assessed in the PK Population as applicable. Anti-drug antibody endpoints will be assessed in the SAF1.

Analysis populations will be summarized with counts and percentages by treatment group to which they were randomized, and overall.

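### Patient-level ADA incidence and onset in SAP 3.6.2 are not treatment-emergent, and the study period they cover is not stated

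*SAP*

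**What the plan says.** SAP 3.6.2 builds patient status from confirmed sample results. A patient is positive with "at least one confirmed positive sample at any time before or during the treatment or post-treatment evaluation periods". A patient is negative if "all evaluated ADA sample results during the treatment and post-treatment evaluation periods are negative" and at least one evaluable result exists after dosing. Everyone else is unknown.

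These statuses are then used as follows:
- By time point: "the ADA incidence (number) and incidence rate (percent) at each evaluated time point will be summarized by treatment".
- By patient: "Similarly, the ADA incidence and incidence rate at patient level will be summarized by treatment".
- The day of the first positive result is listed and glossed as "i.e., onset of ADA development". Onset and maximum titre are summarized by treatment among positive patients.
- Sample results before, during and after treatment are listed.
- ADA status is explored against adverse events in 3.6.2, and it stratifies the concentration summaries and plots in SAP 3.6.1.

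On the analysis set, SAP 3.2.2 states: "Anti-drug antibody endpoints will be assessed in the SAF1". For SAF1 it states: "Patients will be analyzed in the actual treatment group patients received during the Randomized Treatment Period". Safety data from the open-label extension (OLE) go to SAF2. Under SAP 2.1.4, all patients in the OLE receive volanesorsen.

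Protocol 10.6.4 asks for ADA incidence at each time point and "for the overall treatment and post-treatment evaluation period and summarize by treatment period, treatment and dose". SAP 3.6.2 has no split by period, and the list of changes in SAP 3.8 does not mention immunogenicity.

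**The concern.** A reader takes ADA incidence to mean antibodies that appeared after exposure. As defined, the patient-level figure is the share of patients ever positive, including those positive before any drug. Their onset day then precedes the first dose, although it is described as the time antibodies developed.

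The second issue is the window. The status rule sets no limit by period, the analysis set labels patients by what they received in the first year, and placebo patients who continue receive volanesorsen afterwards. The SAP does not say whether their OLE samples feed the patient-level status.

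The outputs at stake are patient-level incidence, onset, maximum titre, the exploratory comparison with adverse events, and the PK output stratified by antibody status. No efficacy result depends on them.

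**Working it through.** The documents state no ADA rate, so there is no planned figure to reproduce. The first three steps compare the rules; the fourth is an illustration on assumed rates.

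**1. Pre-dose positives.** The positive rule includes samples taken before treatment, and 3.6.2 has no baseline-positive, treatment-emergent or titre-rise category. A patient with a stable pre-dose antibody therefore counts once in the patient-level incidence.

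**2. Overlap.** Take a patient who is confirmed positive before dosing and negative in every later sample. The positive rule is met by the pre-dose sample. The negative rule looks only at treatment and post-treatment samples, so it is met too. No precedence is stated.

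**3. Window and set.**
- *OLE samples count.* In favour: the window runs through post-treatment evaluation, which for OLE patients follows open-label dosing (Protocol 6.1.5, SAP 2.1.5). Under the SAF1 grouping, a former placebo patient who converts in the OLE is then tabulated as placebo-positive.
- *OLE samples do not count.* In favour: SAP 3.2.2 and 3.7 tie SAF1 to the randomized period and its follow-up. OLE immunogenicity then has no patient-level summary, although Protocol 10.6.4 asks for summaries by treatment period.

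**4. Size under assumptions.** Let b be pre-dose prevalence, r the conversion rate per year on drug, and s the share of placebo patients who enter the OLE. Assume no conversion on placebo and a full OLE year of exposure.

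- Treatment-emergent, randomized period only: volanesorsen (1-b)r, placebo 0.
- SAP status with OLE samples, placebo: b + (1-b)sr.
- SAP status, volanesorsen with no new OLE positives: b + (1-b)r.
- SAP status, volanesorsen converting at the same rate and share in the OLE: b + (1-b)[(1-s)r + s(1-(1-r)²)].

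With b = 5% and r = 20%, the treatment-emergent figures are 0.95 × 0.20 = 19.0% against 0%, a difference of 19.0 points. Under the SAP status:

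| s | Placebo | Volanesorsen, no new OLE positives | Difference (points) | Volanesorsen, same rate in OLE | Difference (points) |
|---|---|---|---|---|---|
| 0 (no OLE samples) | 5.0% | 24.0% | 19.0 | 24.0% | 19.0 |
| 50% | 14.5% | 24.0% | 9.5 | 31.6% | 17.1 |
| 90% | 22.1% | 24.0% | 1.9 | 37.7% | 15.6 |

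For example, at s = 50%, placebo is 0.05 + 0.95 × 0.50 × 0.20 = 0.145.

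The first row isolates the pre-dose effect. Both arms gain the same 5 points, so the difference stays at 19.0; the ratio becomes 24.0/5.0 = 4.8 where the treatment-emergent placebo rate is zero. Only s > 0 raises placebo alone.

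The two difference columns simplify to (1-b)r(1-s) and (1-b)r(1-sr). Over b = 0-10%, r = 10-30% and s = 50-90%, the true difference (1-b)r is multiplied by 0.1 to 0.5 in the first case and by 0.73 to 0.95 in the second.

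**The case against.** The strongest reply is that no ADA sentence keeps switchers under placebo after Week 52. The explicit both-periods example in SAP 3.2.2 concerns efficacy in the FAS. The whole-study clause under SAF1 concerns patients given volanesorsen by mistake, who are counted under volanesorsen. Where the SAP wants both periods in one set, as in the PK Population, it says so. On that reading the contamination of placebo is zero. This stands as an available reading, but it leaves the window unstated and the OLE without a patient-level summary.

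Second, much can be recovered elsewhere. The time-point table separates visits, and the listings show pre-dose results, first and last positive days and maximum titre. This also stands. It confines the problem to patient-level status and what is derived from it.

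Third, the outputs are descriptive. The adverse-event comparison is exploratory and not stated to be by arm, and the stratified PK output covers only patients who receive volanesorsen. That limits the stakes but does not repair the definitions.

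Fourth, every rate in the illustration is assumed. The SAP says study treatment stopped before the planned period ended, so a full OLE year may not have accrued. The OLE sampling times for ADA cannot be confirmed from the extracted schedule. The figures show direction and range only.

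**Conclusion.** The point holds on the SAP's own wording. Patient-level incidence and onset include antibodies present before dosing, the positive and negative rules overlap, the window is unstated, and the protocol's split by period is missing without being listed as a change.

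A reader might go further and infer that placebo immunogenicity is overstated and the drug effect hidden. The documents do not support that. Pre-dose positives add the same expected amount to both arms and leave the difference unchanged. Inflation of placebo alone needs OLE samples to count, which is plausible but not stated for ADA. If they do count, the assumed 5% pre-dose, 20% on-drug and 50-90% rollover rates reduce a 19.0-point difference to between 1.9 and 17.1 points. The result depends on rollover and on whether the volanesorsen arm also gains positives in the OLE. The actual size cannot be computed from the documents.

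**What to change.** Amend SAP 3.6.2, with matching text in 3.2.2 and 3.8:

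- Report baseline ADA prevalence by arm as its own line.
- Define treatment-emergent ADA as negative at baseline and confirmed positive after the first dose or, for patients positive at baseline, a titre rise of a size fixed in advance.
- Make positive, negative and unknown mutually exclusive, and state where a patient positive only before dosing belongs.
- Report patient-level incidence and onset for the randomized period by arm in SAF1.
- Report the OLE separately in SAF2, with the first volanesorsen dose as time zero for former placebo patients. SAP 3.2.3 uses one baseline for both periods, so ADA needs a stated exception for these patients.
- Use the treatment-emergent status in the adverse-event comparison, and say which status stratifies the PK output.
- List any remaining departure from Protocol 10.6.4 in SAP 3.8.

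The change uses samples already planned. It costs a few extra derivations and tables, and the sponsor must choose the titre-rise threshold before the tables are run.

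### Concentration tables and plots appear to be stratified by ever-positive ADA status, which dilutes early-visit differences, and the ADA-adverse event comparison has no timing rule

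*SAP*

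**What the plan says.** SAP 3.6.2 defines ADA status at two levels.

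- **Patient level.** A patient is positive with "at least one confirmed positive sample at any time before or during the treatment or post-treatment evaluation periods". A patient is negative "if all evaluated ADA sample results during the treatment and post-treatment evaluation periods are negative", provided there is at least one evaluable post-dose result. All others are unknown.
- **Sample level.** Each sample is screened and confirmed, and its third category is different: "Sample ADA status (screen positive/negative, confirmed positive/negative or unevaluable".

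For pharmacokinetics, SAP 3.6.1 says that trough and post-treatment concentrations "will be summarized by study day, with and without stratification by IM status (positive/negative or unknown), using descriptive statistics". It also plans "plasma volanesorsen concentration-time plots with stratification by anti-drug antibody status". Onset of positivity (Tfirst) appears beside each concentration in the listing. Tfirst and the last positive day (Tlast) are listed per patient in 3.6.2, and onset is summarised there. No concentration table or plot is split at onset.

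For safety, 3.6.2 has one sentence: "Potential relationships between anti-drug antibody results (e.g., ADA status) and AE incidence will be evaluated in an exploratory manner".

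**The concern.** A label set by any positive sample at any time uses information from after the measurement it classifies. A Day 22 trough in a patient who first turns positive on Day 358 would be summarised as ADA-positive. The comparison then sets patients who at some time become positive against patients who never do. That is not the same as comparing antibody present with antibody absent.

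A reader of the by-day tables could conclude that antibodies barely affect exposure, or that their effect grows with time, when the label alone produced that pattern. For adverse events, a patient followed longer has more chance both of an event and of a positive sample.

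Elsewhere the SAP does align timing. Section 3.7.2.3 relates bleeding to anticoagulant or antiplatelet drugs only if the drug was in use at bleeding onset.

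**Working it through.** The plan states no figure for the ADA analyses, so there is nothing to reproduce. The check is a reading of the text followed by two illustrations. Onset times, effect sizes, event rates and dropout are not in the documents and are assumed over ranges.

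**Which status stratifies the concentrations?** SAP 3.6.1 gives the strata as positive, negative or unknown. Patient status has those levels: "Patient ADA status (positive/negative or unknown) for all evaluable patients". Sample status has unevaluable as its third level. The concentration listing in 3.6.1 also carries patient ADA status. Patient-level, ever-positive status is therefore the most natural reading, though the SAP does not say so outright.

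**Dilution in the by-day concentration summaries.** Let R be the true geometric mean ratio once antibodies are present, and F(t) the share of ever-positive patients already positive at day t. Pre-onset samples are assumed to match those of negative patients, and antibodies are assumed to persist. Then

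- observed ratio at day t = R^F(t)
- F(t) = [1 − exp(−λt)] / [1 − exp(−358λ)], with λ = ln 2 / median onset (exponential onset, truncated at Day 358)

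Example with median onset at Day 176 and t = 85: λ = 0.693/176 = 0.00394. F = (1 − 0.716)/(1 − 0.244) = 0.38. With R = 4, the observed ratio is 4^0.38 = 1.69.

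| Median onset | R | Day 22 | Day 85 | Day 176 | Day 358 |
|---|---|---|---|---|---|
| Day 85 | 2 | 1.13 | 1.44 | 1.75 | 2.0 |
| Day 176 | 2 | 1.08 | 1.30 | 1.58 | 2.0 |
| Day 260 | 2 | 1.07 | 1.26 | 1.53 | 2.0 |
| Day 85 | 4 | 1.27 | 2.08 | 3.05 | 4.0 |
| Day 176 | 4 | 1.16 | 1.69 | 2.50 | 4.0 |
| Day 260 | 4 | 1.14 | 1.58 | 2.33 | 4.0 |

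Dilution is strong early and absent at Day 358, because by then every patient labelled positive has become positive. Classing each sample by its status on the day recovers R at every visit by construction.

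**Adverse events with no true antibody effect, if the patient label were used.** Simulation of 400,000 patients over 358 days:

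- ADA sampling assumed at Days 22, 50, 85, 176, 260 and 358
- median onset Day 176 or 358
- 0.5 or 1 event per year, independent of ADA
- dropouts leaving uniformly between Day 7 and Day 358
- negative patients required to have reached Day 22

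| Dropout | Incidence ratio, ever-positive vs negative | Rate ratio, time split at first positive sample |
|---|---|---|
| 0% | 1.00 | 1.00 |
| 20% | 1.10-1.19 | 0.99-1.01 |
| 40% | 1.19-1.34 | 0.98-1.01 |

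For example, with 40% dropout, median onset Day 176 and 0.5 events per year, incidence is 35.6% against 26.5%, and 0.356/0.265 = 1.34. Across all scenarios, 52-62% of first events in ever-positive patients came before antibodies were detected.

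**Is follow-up unequal here?** It can be. Protocol 3.4 allows up to 3 years on study, the second extension year is optional (Protocol 3.4.3), and SAP 3.1 records that treatment stopped before the planned end.

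**The case against.** The strongest objection concerns adverse events. A reader might infer that the SAP compares adverse events by ever-positive status and so will create a false association. The documents do not support that. ADA status is given only as an example in an exploratory sentence, and no table, test or timing rule is fixed. Adverse event summaries are split by analysis period (SAP 3.7), which limits differences in follow-up. With complete follow-up the null ratio is 1.00. What stands is that the method is unspecified, that the patient label is the likely default, and that bias is possible if follow-up is unequal.

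A reader might also carry the idea of a falsely created effect over to the concentration tables. There, misplaced pre-onset samples only dilute a difference. Nor can the matter be put as lost power or excess false positives, because the SAP plans only descriptive or exploratory outputs here and no hypothesis test.

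Two further objections have some force. The stratifier is inferred: 3.6.2 also uses negative, positive and unknown for incidence at each time point, so matching the category names is not conclusive. And the listings show onset beside each concentration, so pre- and post-onset values can be read patient by patient. What is missing is a summary or plot that uses onset.

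**Conclusion.** The point holds for concentrations on the most natural reading of SAP 3.6.1. Early-visit ADA differences are diluted: on the assumed inputs a true 4-fold ratio shows as 1.58-2.08 at Day 85 and 2.33-3.05 at Day 176, and a 2-fold ratio as 1.26-1.44 and 1.53-1.75. The dilution disappears by the last visit if antibodies persist.

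For adverse events the finding is a missing classifier and timing rule. The null incidence ratios of about 1.1-1.3 apply only if the patient label is used and 20-40% drop out. All sizes rest on assumed onset, effect, event and dropout patterns.

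The affected outputs are descriptive or exploratory. The primary and secondary endpoints are untouched.

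**What to change.** **SAP 3.6.1.** Add, or use instead, a concentration table and plot that class each sample by ADA status at its date. Use the most recent ADA result at or before the sample, so that samples before Tfirst are negative. State a rule using Tlast for transient positives: Protocol 10.6.4 recognises transient status, and treating patients as positive for ever after Tfirst would misclassify them in the other direction.

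**SAP 3.6.2.** Report adverse events and person-time before and after Tfirst. Keep ever-positive status for the patient-level ADA incidence table. In the same edit, say how to class a patient who is positive only before dosing, since the positive and negative rules as written both fit that patient.

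**Cost.** Wording and programming only. Sample dates, event dates, Tfirst and Tlast are already collected or derived. ADA-positive strata will be small at early visits. Onset is known only to the ADA sampling interval, and ADA is sampled less often than concentration (about 7 against 10 time points in the randomized period of Protocol Appendix A), so some troughs will rely on an earlier ADA result.
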